5.1.5 Analysis window

The study days is defined as the days from the first dose of study drugs to the safety/efficacy evaluation. The day of first dose of study drugs (SHR-1210 or apatinib, whichever is used first) is used as the start date of the study (Day 1).

The study date is calculated as follows:

Study days = evaluation date – start date of study + 1, in the case of evaluation after the first dose of study drugs

Or

Study date = evaluation date – start date of study, in the case of evaluation before the first dose of study drugs.

Data obtained from post-baseline visits will be summarized by protocol visits of SHR-1210 shown in eCRF. There is no need to consider whether the visit window specified by the protocol has been exceeded.

5.1.6 Missing data

5.1.6.1 Medical history

For disease-related records before the first dose of study drugs:

- If the day is missing, the day will be imputed with the 1st of the month;
- If the month and day are missing, the day will be imputed with 1 Jan.;
- If the date is completely missing, the day will not be imputed.

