5.1.4 Covariates and subgroups

Subgroup analysis of the primary endpoint ORR will be based on the FAS:

- Sensitive recurrence: progress in ≥ 90 days from the last chemotherapy
- Drug-resistant recurrence: progress during chemotherapy or within 90 days from the last chemotherapy

The time between progress and the last chemotherapy is calculated as follows: date of the most recent progress/relapse – date of the last chemotherapy. Sensitive recurrence is determined if the time between progress and the last chemotherapy is \geq 90 days; otherwise, drug-resistant recurrence is determined.

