5.4.4 Subgroup analysis

Based on the FAS, the following subgroup analyses will be performed on the primary efficacy endpoint ORR, as well as the secondary endpoints OS, PFS, and 6/12-month OS rates:

- Sensitive recurrence: progress in \geq 90 days from the last chemotherapy
- Drug-resistant recurrence: progress during chemotherapy or within 90 days from the last chemotherapy

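### The earliest-date imputation rule, combined with a default to drug-resistant, can misclassify relapse type when a pre-study date is incomplete

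*SAP*

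**What the plan says.** SAP 5.1.6.1 (Medical history) opens with its scope: "For disease-related records before the first dose of study drugs". Three rules follow. Where the day alone is unknown, the SAP states: "If the day is missing, the day will be imputed with the 1st of the month". Where the month is unknown as well, it states: "If the month and day are missing, the day will be imputed with 1 Jan". A wholly unknown date is left as it is: "If the date is completely missing, the day will not be imputed".

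SAP 5.1.4 (Covariates and subgroups) defines the interval that sets relapse type: "The time between progress and the last chemotherapy is calculated as follows", namely "date of the most recent progress/relapse – date of the last chemotherapy". An interval of 90 days or more is sensitive; "otherwise, drug-resistant recurrence is determined".

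SAP 5.4.4 applies this split to ORR ("the following subgroup analyses will be performed on the primary efficacy endpoint ORR"), and also to OS, PFS and the 6- and 12-month OS rates. Protocol 10.5.6 names the same two subgroups and leaves any others to the SAP, which adds none.

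The date of the most recent progression is a collected pre-dose disease item (SAP 5.2.2.2). No other imputation rule in the SAP addresses it.

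**The concern.** Two one-sided choices act in the same direction. An incomplete progression date is moved as early as it can go, which shortens the interval. The classification rule then reads any short, zero or negative interval as drug-resistant. Read literally, it does the same with an interval that cannot be computed because the progression date is wholly missing and so left unimputed.

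Elsewhere the SAP ties imputed dates to known ones: AE onset to first dose (5.1.6.2), death to the last survival date (5.1.6.5), and new anti-tumor treatment to progression, last dose and end dates (5.1.6.6). The date that defines the subgroups has no such tie.

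At stake is the make-up of the only two pre-specified subgroups, and so the ORR, OS, PFS and OS rates reported for each.

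**Working it through.** The plan states no figure on this point, so there is none to reproduce. The check applies SAP 5.1.6.1 and then SAP 5.1.4 to known dates.

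**Inputs.** Imputation to the 1st of the month or 1 January (SAP 5.1.6.1). Cut-off of 90 days (SAP 5.1.4). Assumptions, because the documents give no distribution: progression equally likely on each day of 2018; true sensitive intervals uniform from 90 days to an upper limit U of 150, 180, 270 or 365 days.

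**Progression day missing.** A progression on day d of a month moves back d − 1 days, at most 30. A true interval g is mislabelled if g − (d − 1) < 90, so only g from 90 to 119 is at risk. Example: 20 Feb to 25 May 2018 is 94 days; imputed to 1 May it is 70, hence resistant. The mean day of the month in 2018 is 5738/365 = 15.72, so on average 14.72 interval values are mislabelled. With U = 180 there are 91 values: 14.72/91 = 16.2%.

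**Progression month and day missing.** The shift is up to 364 days, so g from 90 to 453 is at risk. If chemotherapy ended in the same calendar year, 1 January is on or before it and the interval is zero or negative. Example: 20 Feb to 20 Aug 2018 is 181 days; imputed to 1 January it is −50. For 2018 progressions, any last chemotherapy after 3 Oct 2017 gives the same result. With U = 180, the progression on day k of the year mislabels min(k − 1, 91) of the 91 values: (4095 + 274 × 91)/(365 × 91) = 29029/33215 = 87.4%.

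Share of sensitive relapses mislabelled, **per incomplete progression date**:

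| U (days) | Day missing | Month and day missing |
|---|---|---|
| 150 | 24.1% | 91.5% |
| 180 | 16.2% | 87.4% |
| 270 | 8.1% | 75.1% |
| 365 | 5.3% | 62.1% |

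A simulation with exponential intervals (assumed medians 60, 90 and 120 days) gives about 15%, 10% and 8% with the day missing, and about 77%, 66% and 58% with month and day missing. When only the progression date is incomplete, no resistant relapse becomes sensitive.

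**Chemotherapy date incomplete, if the rule covers it.** The interval lengthens. Among resistant relapses with true intervals of 0 to 89 days, 16.4% (day missing) or 87.5% (month and day missing) become sensitive. If both dates lack only the day, the shifts partly cancel: 1.5% of sensitive relapses (90 to 180 days) and 13.8% of resistant ones are mislabelled.

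**Would a floor at the last chemotherapy date be enough?** No. The floored interval is 0 days, still below 90, and 16.2% and 87.4% are unchanged.

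**Effect on a subgroup.** The documents do not give the split, so assume 22 per subgroup, about half of 45. Near 30% ORR, 7/22 = 31.8%: losing one responder gives 6/21 = 28.6% (−3.2 points) and gaining one gives 8/23 = 34.8% (+3.0). Near 15%, 3/22 = 13.6%: 2/21 = 9.5% (−4.1) and 4/23 = 17.4% (+3.8).

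**The case against.** The strongest reply is that few dates will be incomplete. Inclusion criterion 5 (protocol 5.1) requires progression on imaging, so a dated scan should exist. The time of the last anti-tumor treatment must be recorded (protocol Table 1, note 2). Protocol 11.1.2 forbids blank CRF items, and 11.2 provides source data verification. A missing month should be rare, and a missing day matters only for intervals of 90 to 119 days. This stands: the percentages above are per incomplete date, not per subject.

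Coverage is also inferred. The rule sits under Medical history, which in SAP 5.2.3 refers to coded prior illnesses, while progression and chemotherapy dates are handled in 5.2.2.2 and 5.2.4.1. The reference to disease-related records still fits the progression date best, and no other rule covers it.

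Finally, these are descriptive subgroups in a study that disclaims hypothesis testing (SAP 3), and a 3 to 4 point shift is small beside the 95% Clopper-Pearson interval for 7/22, about 14% to 55%. That limits the priority, but does not make the rule right.

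A reader might infer more than the documents support:

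- That sensitive relapses will in general be turned into resistant ones. No count of incomplete dates is given, and an incomplete chemotherapy date reverses the error.
- That the missing check against chemotherapy is the cause. The floor calculation shows that it is not; the early date and the default class are.
- That the resistant subgroup's ORR and OS would be inflated by better-prognosis subjects. Neither document reports outcome by relapse type.
- That relapse type is already on record from screening. Criterion 5 admits both types, randomization names no stratification (protocol 7.1.3), and the screening table has no such field.

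**Conclusion.** The point holds as a conditional one: SAP 5.1.6.1 and 5.1.4 together can mislabel relapse type when a date is incomplete. This is a stated rule that gives wrong classes, not merely missing detail. It rests on reading the rule as covering the progression date. Under the assumptions shown, 5% to 24% of sensitive relapses are mislabelled per progression date missing its day, and 58% to 92% per date missing month and day. The net direction across subjects is not fixed.

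Only the sole pre-specified subgroups are affected. The ORR in all subjects and the rule of at least 9 responders in 40 do not depend on relapse type. Minor to moderate priority.

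**What to change.** In SAP 5.1.4, state that subgroup classification does not use the earliest-date rule of 5.1.6.1. Instead:

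1. Compute the interval at the earliest and latest possible dates, with progression not before the last chemotherapy (unless progression on chemotherapy is recorded) and not after first dose. Classify if both give the same type.
2. If they differ, use the relapse type in source documents where recorded; otherwise use the midpoint of the bounded range, or report the subject as undetermined.
3. Apply the same rule to an incomplete last-chemotherapy date, and say so.
4. Do not let a missing interval default to drug-resistant.
5. Repeat the subgroup ORR without subjects whose dates were imputed.

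Under the exponential assumptions, the bounded midpoint lowers total misclassification per incomplete progression date from about 5% to 3% (day missing) and from 27–35% to about 14% (month and day missing). The second gain depends on first dose following progression closely (14 to 60 days was assumed in checking it). If the range is bounded above only by the year end, the total is 28–43%, which is no improvement overall. Undetermined is therefore the safer choice when the month is missing and first dose does not narrow the range.

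The cost is a few SAP sentences and one sensitivity row before database lock, with no new data collection. A few subjects may be left undetermined, and with the day missing the midpoint moves about 3% of resistant relapses to sensitive.

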5.1.6.2 Adverse Event

- If the day of the onset date is missing, and the year and month are the same as those of the first dose, the day will be imputed with the date of first dose; otherwise, it is imputed with the 1st of the month;
- If the month and day of the onset date are missing, and the year is the same as those of the first dose, the day will be imputed with the date of first dose; otherwise, it is imputed with 1 Jan. of the year;

- If the onset date is completely missing, the day will be imputed with the date of first dose;
- If the day of the end date is missing, the day will be imputed with the last day of the month or the date of death (if applicable), whichever is earlier;
- If the year or month of the end date is missing, the day will not be imputed.

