9.1.1 Definition of AE

AE refers to any untoward medical condition in a clinical study subject who receives a pharmaceutical product, and the condition does not necessarily have a causality with the treatment. All AEs from signing of the informed consent form to the end of the safety follow-up period (90 days after the last dose) or the start of other anti-tumor treatments will be collected in this study. AEs can include any unfavorable and unintended symptoms, signs, abnormal laboratory findings, or diseases, including the following:

- 1) Worsening of pre-existing (prior to entering the clinical trial) medical conditions/diseases (including worsening symptoms, signs, or laboratory abnormalities);
- 2) Any new AE: Any new adverse medical conditions (including symptoms, signs, and newly diagnosed diseases);
- 3) Clinically significant abnormal laboratory findings.

All AEs should be documented in detail by the study personnel, including: the name of the AE and description of all relevant symptoms, onset time, severity, causality assessment, duration, measures taken, as well as final results and outcomes.

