5.1.6.3 Concomitant medications

The dates of concomitant medications are imputed in the same way as AEs.

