- If YYYY = min (year) [max (PD date + 1, date of the last dose + 1), end date of new anti-tumor treatment], and MM = min (month) [max (PD date +1, date of the last dose +1), end date of new anti-tumor treatment], the date imputed = min [max (PD date + 1, date of the last dose + 1), end date of new anti-tumor treatment].
- If YYYY = min (year) [max (PD date + 1, date of the last dose + 1), end date of new anti-tumor treatment], and if at the same time MM > min (month) [max (PD date +1, date of the last dose +1), end date of new anti-tumor treatment], then the imputed date = 1 MM, YYYY.
- If YYYY < min (year) [max (PD date + 1, date of the last dose + 1), end date of new anti-tumor treatment], then the day of the imputed date is the last day of MM.
- If YYYY > min (year) [max (PD date + 1, date of the last dose + 1), end date of new anti-tumor treatment], then the imputed date = 1 MM, YYYY.

All imputed dates must be before the date of withdrawal of informed consent form, lost to follow-up, and death.

Missing data of laboratory evaluations are not imputed.

The rules for imputation of missing data for the remaining study endpoints will be detailed in the specific sections of analyses.

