5.5.1 Adverse events

Adverse events (AEs) will be analyzed based on the treatment-emergent adverse events (TEAEs):

- 1) All AEs that occur from the first study dose to 90 days after the last dose;
- 2) An AE that starts before the first study dose but worsens after administration.

Treatment-related AEs are defined as TEAEs with a causality of definitely related, possibly related, or indeterminable. If the relationship between an AE and the study drug is missing, the AE will be considered as a treatment-related AE.

All AEs will be coded with MedDRA 21.0. and graded by NCI-CTCAE v4.03. For the same SOC and/or PT, multiple cases of the same events that occur in one subject will be counted only once. For the same AE reported in one subject multiple times but varying in CTCAE grade, the AE of the greatest grade will be enumerated.

The incidence of AEs will be sorted from high to low based on their corresponding SOC in the SHR-1210 200 mg, IV, Q2W + apatinib 375 mg (or apatinib 250 mg), PO, QD group. The incidence of AEs in each SOC will be sorted from high to low based on their PT. If the incidences of \geq 2 PTs are equal, the AEs will be sorted alphabetically. If there is no AE under a SOC or PT, then analysis is not conducted.

The number of TEAE cases as well as the number of subjects based on the SS will be summarized in a table by dose group. The summary table should at least include the number of subjects with at least one TEAE/SAE/, TEAEs leading to treatment discontinuation, TEAEs leading to dose interruption or dose reduction, SAEs, SAEs leading to death, TEAEs of special interest, immune-related TEAEs (irAEs), and CTCAE grading. For all categories included in the summary table, CTCAE Grade ≥ 3 TEAEs and treatment-related AEs with an incidence of $\geq 5\%$ will be summarized by SOC and PT, respectively. Laboratory abnormalities with an incidence of $\geq 10\%$ will be summarized. TEAEs leading to treatment discontinuation, TEAEs leading to dose interruption or dose reduction, and all treatment-related AEs will be analyzed respectively for SHR-1210 and apatinib. An immune-related AE is determined in the case of an indeterminable immune-related AE.

In particular, the incidences and outcomes of AEs assessed per the CTCAE 4.03 below are separately analyzed:

- Hematologic toxicity
 - Grade 4, or
 - Grade ≥ 3 thrombocytopenia with hemorrhage, or
 - Grade ≥ 4 neutropenia with pyrexia and infection

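### SAP 5.1.6.2 imputes missing AE onset to the first dose without checking the AE end date, so a screening event that ended before dosing can be counted as treatment-emergent

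*SAP*

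**What the plan says.** SAP 5.1.6.2 has three branches that put AE onset on the first-dose date:

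- onset wholly missing: "If the onset date is completely missing, the day will be imputed with the date of first dose";
- day missing, under the condition "If the day of the onset date is missing, and the year and month are the same as those of the first dose";
- month and day missing, under the condition "If the month and day of the onset date are missing, and the year is the same as those of the first dose".

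Partial onsets in any other month or year go to the first of that month or to 1 January. The end date is imputed separately: a missing end day goes to month-end, capped only by an earlier death. Nothing links the two dates.

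SAP 5.1.6.6 closes with an ordering check, "All imputed dates must be before the date of withdrawal of informed consent form, lost to follow-up, and death". It mentions neither the AE end date nor the first dose.

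Protocol 9.1.1 collects "All AEs from signing of the informed consent form to the end of the safety follow-up period". SAP 5.5.1 analyses AEs as TEAEs, whose first limb is "All AEs that occur from the first study dose to 90 days after the last dose". The second limb covers events that began earlier and got worse after dosing. AE incidence is a primary endpoint (SAP 4.1). For drugs, SAP 5.1.6.3 says "The dates of concomitant medications are imputed in the same way as AEs".

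**The concern.** Moving an unknown onset to the first dose is a sensible default when it is unclear whether the event came before or after treatment. It is not sensible when the record itself answers that question. If the end date is known and lies before the first dose, the event was over before treatment began, whatever its onset. The rule as written still assigns the first-dose date. This produces an interval that ends before it starts, and it places the event inside the TEAE window.

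What is at stake is the accuracy of a descriptive primary endpoint, with the error always towards too many TEAEs. SAP 5.5.1 also counts an AE with missing causality as treatment-related, so an incomplete screening record could reach the treatment-related tables as well.

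**Working it through.** The plan gives no figure for incomplete dates, so there is none to reproduce. The check applies the stated rules to example records.

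**Inputs.** Onset and end-date rules: SAP 5.1.6.2. TEAE window: SAP 5.5.1. AE collection from consent: Protocol 9.1.1. Screening on days -28 to -1: Protocol 7.2.1. Group sizes of 6 per Stage I group and 39 in Stage II: SAP 2.1. Assumed for illustration: first dose 20 Jun 2018, last dose 1 Dec 2018.

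**Rule.** Imputed onset = first dose in the three branches above. The event is a TEAE if first dose ≤ onset ≤ last dose + 90 days.

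| Recorded onset | Recorded end | SAP onset | Onset after end? | TEAE under SAP | TEAE with end-date check |
|---|---|---|---|---|---|
| blank | 12 Jun | 20 Jun | yes, by 8 days | yes | no |
| Jun 2018 | 12 Jun | 20 Jun | yes, by 8 days | yes | no |
| 2018 | 12 Jun | 20 Jun | yes, by 8 days | yes | no |
| May 2018 | 12 Jun | 1 May | no | no | no |
| blank | 2 Jul | 20 Jun | no | yes | yes |
| blank | missing | 20 Jun | not applicable | yes | yes |
| blank | Jun 2018 (set to 30 Jun) | 20 Jun | no | yes | yes |

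The first three rows show the fault. Those events ended before dosing and cannot meet the second TEAE limb, so the imputed date alone makes them TEAEs. The fourth row shows that a partial onset in an earlier month is unaffected. The last three rows show that an end-date check keeps the cautious default wherever timing is in real doubt.

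**Reach of the branches.** Assume screening onsets spread evenly over days -28 to -1 and first doses spread evenly over 365 days, giving 365 × 28 = 10,220 pairs. The onset falls in the first-dose month in 7 × 462 + 4 × 434 + 378 = 5,348 pairs (months of 31, 30 and 28 days), or 52%. It falls in an earlier year in 28 × 29 / 2 = 406 pairs, so in the same year in 96%. These are the shares of day-missing and of month-and-day-missing screening onsets that move to first dose. They are not misclassification rates, because the event must also have a recorded end before dosing.

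**Size per subject.** The selected group has 6 + 39 = 45 subjects.

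- One extra subject in the selected group: 1/45 = 2.2 points.
- One extra subject in a Stage I group of 6: 1/6 = 16.7 points.
- At the 5% cut for tabulating treatment-related AEs in SAP 5.5.1: 2/45 = 4.4% becomes 3/45 = 6.7%, so one false case can bring a term into the table.

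SAP 5.5.1 counts a subject once per preferred term, so each increment applies only if the subject has no other event of that term.

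**Comparison within the SAP.** In 5.1.6.6 a wholly missing start of new anti-tumor treatment is set to min[max(PD date + 1, last dose + 1), end date of that treatment]. The SAP therefore already caps one imputed start by its own end date. The AE rule lacks the same cap.

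**The case against.** The strongest reply has three parts.

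- **The triggering record is rare.** Protocol 9.1.1 requires an onset time for every AE, Protocol 11.1.2 requires complete CRF entry with queries on illogical data, and Protocol 11.3.3 reviews missing values before lock. The record needs an incomplete onset together with an end known to precede dosing, within a screening period of at most 28 days. This stands as a limit on frequency. It does not supply the missing bound.
- **The TEAE wording could exclude such an event,** since something that ended before dosing did not occur after it. But the SAP names no date other than the imputed onset for placing the event, and it does not say that a recorded end overrides it. If that is the intention, one sentence would settle it.
- **The error is conservative and descriptive.** It over-counts toxicity, and SAP 3 sets no safety threshold or test. This stands, and it is why the point is minor.

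A reader might infer three stronger claims that the documents do not support. First, that a drug stopped before dosing would be reclassified from prior to concomitant: the SAP has no start-date rule separating the two, and 5.2.4.2 plans only a list. Second, that the choice of Stage II regimen could be distorted by 16.7 points: SAP 6 bases that review on listings of AEs and laboratory evaluations, not on TEAE incidence. Third, that every false TEAE raises an incidence: it does not when the subject already has the same term on treatment.

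**Conclusion.** The gap is real. Applied literally, SAP 5.1.6.2 gives a screening AE that ended before dosing an onset after its end and counts it as a TEAE, which inflates a primary safety endpoint. The conclusion rests on the programmed TEAE flag following the imputed onset, as the SAP text implies.

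The effect is 2.2 points per affected subject and preferred term in the selected group of 45, or 16.7 points for a Stage I group of 6 in the final tables, in each case only where the subject has no other event of that term. These denominators assume that every planned subject enters the safety set. The documents give no frequency of incomplete dates, so no total can be stated; it is probably small. This is a minor correction that does not bear on the Stage I decision or the response-based development criterion.

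**What to change.** Amend SAP 5.1.6.2 as follows:

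- Impute onset to the first-dose date only if the AE end date is missing, the event is ongoing, or the end date is on or after first dose.
- If the known end date, or the latest date its known parts allow, is before first dose, impute the earliest date consistent with the known onset parts, no earlier than consent and no later than the end date. If onset is wholly missing, use the consent date. Class the event as non-TEAE.

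In the example, with consent on 23 May 2018 (28 days before 20 Jun) and an end on 12 Jun, the onsets become 1 Jun for Jun 2018, 23 May for 2018, and 23 May for a blank. All precede dosing.

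Carry the same end-date bound to 5.1.6.3, solely so that the medication listing shows no start after its stop.

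The cost is a sentence or two in the SAP and about one line of code, to be done before database lock. The conservative default is kept wherever the timing is uncertain.
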